1.7. Benefit-Risk Assessment

Overall, BEM was well tolerated across the entire development program. At 550 mg BID in the Phase 2 and CV43043 studies, the safety profile was comparable to placebo. AEs reported were generally mild to moderate in severity and self-limiting. Available data from the BEM clinical pharmacology program suggest a low DDI potential. At dose levels ≥825 mg BID, an increase in GI-related AEs (mostly nausea and vomiting) was observed, which were mild to moderate in severity. GI AEs were more frequent at the 1100 mg BID dose and resulted in early treatment discontinuation. SAEs were only reported in the COVID-19 Phase 2 and Phase 3 studies (none in Phase 1 healthy volunteer studies), assessed as not related to study treatment, and tended to describe progression or complications of COVID-19; SAEs resulting in death have only been reported in subjects receiving placebo. The clinical efficacy data at 550 mg BID from the truncated study CV43043 indicate a benefit in reduction of hospitalizations (71%), COVID-19 complications, and medically attended visits. This clinical benefit was observed consistently across sub-analyses in several populations within the study.

Furthermore, the nonclinical safety profile of BEM was similarly favorable, as assessed in a comprehensive non-clinical safety program. There were no target organs identified in 2- and 13-week toxicity studies. BEM is non-mutagenic, has no effect on reproductive performance and is non-teratogenic.

Based on the totality of the data, BEM at 550 mg BID has demonstrated a favorable benefit-risk profile for evaluation in patients with COVID-19.

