endpoints included hospitalization, all-cause mortality and change in viral load. At the time of discontinuation, 216 patients had been randomized (2:1; active:placebo), with 207 patients included in the efficacy evaluable population. The study enrolled a broad outpatient population, with 47% who were high risk, 28% who were vaccinated, and 56% who were seropositive at baseline. Because the study was prematurely discontinued, no formal statistical comparisons were made and results are presented descriptively. Although the primary endpoint of symptoms alleviation or improvement was not met, a lower proportion of patients required hospitalization for COVID-19 (secondary endpoint) in the BEM arm (2.9%; 4/137 patients) compared to the placebo arm (10%; 7/70 patients). This represents a 71% reduction in hospitalization in patients who received BEM. This clinical observation favoring the BEM arm was consistent for the clinical outcome secondary efficacy endpoints, including COVID-19 related medically attended visits (10.2% vs 14.3%; BEM vs placebo), COVID-19 related complications (4.4% vs 10.0%) and post-treatment infections (9.5% vs 14.3%). There were no deaths in the study. There was no meaningful difference in the change from baseline in viral load between the BEM arm and the placebo arm. In addition, the safety and tolerability of the 550 mg BID dose was generally comparable to placebo. There were no drug-related serious adverse events (SAEs) reported, and proportions of patients with adverse events (AEs) leading to study drug discontinuation were low (2.8% in the BEM arm vs 7.0% in the placebo arm). Overall, gastrointestinal (GI) AEs were 11.3% in the BEM arm vs. 9.9% in the placebo arm. There were more drug-related GI AEs (nausea, diarrhea, abdominal discomfort/pain) in the BEM arm (9.2%) compared to placebo (1.4%), but all were low grade (mild/moderate) and none resulted in treatment discontinuation. There was no reported vomiting in the BEM arm.

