7. ADVERSE EVENTS

7.1. **Definitions**

An AE is defined as any untoward medical occurrence in a subject administered a medicinal product(s) and which does not necessarily have to have a causal relationship with this treatment. An AE can therefore be any unfavorable and unintended sign (for example, an abnormal laboratory finding), symptom, or disease temporally associated with the use of a medicinal product(s), whether or not considered related to this medicinal product(s).

A suspected adverse reaction is any AE for which there is a reasonable possibility that the drug(s) caused the AE. 'Reasonable possibility' means there is evidence to suggest a causal relationship between the drug(s) and the AE. A suspected adverse reaction implies a lesser degree of certainty about causality than adverse reaction, which means any AE caused by a drug(s).

An AE may be:

- A new illness
- Worsening of a previous chronic illness or a concomitant illness
- An apparent adverse effect of the study medication(s) on safety-related laboratory tests. This observation could include a clinically-significant abnormal laboratory value or a significant shift from baseline (though still within normal range) which the clinical investigator or qualified designate considers to be clinically significant

Surgical procedures themselves are not AEs. They are therapeutic measures for conditions that required surgery. The condition for which the surgery is required is an AE, if it occurs or is detected during the study period. Planned (elective) surgical measures and the conditions(s) leading to these measures are not AEs, if the condition(s) was (were) known before the start of study treatment. In the latter case, the condition should be reported as medical history.

An SAE or reaction is any untoward medical occurrence that at any dose:

- Results in death
- Is life-threatening
- Requires inpatient hospitalization or prolongation of existing hospitalization
- Results in persistent or significant disability or incapacity (defined as a substantial disruption of a person's ability to conduct normal life functions)
- Is a congenital anomaly or birth defect
- Is an important medical event that may jeopardize the subject or may require intervention to prevent one of the other outcomes listed above (according to medical judgment of the qualified investigator)

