4.3. Sample Size Considerations

The primary endpoint of proportion of subjects with all-cause hospitalization and all-cause mortality through Day 29 will be compared between treatments using a Cochran-Mantel-Haenszel (CMH) test adjusted for the stratification factors of age and region. The overall type I error will be controlled at a one-sided 0.025 level. Total beta spending was specified at a 0.10 level.

The study was planned to have interim analyses at 30% (futility only) and 65% (futility, safety and efficacy) of the originally planned number of subjects. The interim analyses were removed due to fast enrollment such that the final sample size was reached prior to the first planned interim analysis.

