4.3.1. Sample Size Justifications

Assuming the combined all-cause hospitalization and all-cause mortality rate will be 4% in the placebo arm, the sample size needed to detect a true 60% reduction (corresponding to an absolute difference in rates of 2.4%) in the BEM treatment arm with 90% power at a 1-sided significance

level of 2.5% was determined to be 1982 randomized participants in the supportive-care-only population. Sample size was calculated using SAS (version 9.4) for a 2-sample proportion Chisquare test. Considering the planned interim analyses with both alpha and beta spending according to Lan-Demets approximation of O'Brien Fleming method the sample size should be inflated by a multiplier of 1.055 to a target sample size of 2100 participants (see Section 11.1). Assuming 95% of randomized subjects who receive only supportive care as SOC will meet the mITT-S population criteria (see Section 6.5.4), the study targets total enrollment of 2210 subjects in the supportive-care-only population. If the true rate in the placebo arm is 3%, and assuming a reduction of 60% with BEM, the planned study has at least 80% power to detect a treatment effect. Planned enrollment in the combination arm is up to 300 subjects.

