8.9. Summary of Reasons for Efficacy Non-Evaluability/Exclusion from Efficacy Analyses

Reasons for exclusion from mITT populations will be tabulated. Categories include did not receive study drug and did not have ≥ 1 positive SARS-CoV-2 result through Day 5 (from central testing on NP swab samples).

9.

Atea Pharmaceuticals, Inc. Statistical Analysis Plan – AT-03A-017

SAFETY AND TOLERABILITY

9.1. **Overall Summary of Tolerability**

All adverse events will be coded according to the Medical Dictionary for Regulatory Activities (MedDRA) and will be summarized by treatment group for the safety population. Only treatment-emergent adverse events (TEAEs) will be summarized. Treatment-emergent adverse events are those with start date/time within the treatment period, defined as the time from first study drug administration to Day 29. Events that occur after Day 29 with relationship to study drug recorded as 'related' will also be considered treatment-emergent. If the AE onset date is missing or partial, the conventions described in Section 6.8.3 will be used to determine if the event is treatment-emergent.

Adverse event severity will be graded according to the Division of AIDS (DAIDS) Table for Grading the Severity of Adult and Pediatric Adverse Events, Version 2.1 dated July 2017⁶.

An overall summary of TEAEs will be presented and include tabulations (number and %, unless otherwise indicated) for the following:

- Subjects with at least one TEAE, overall and by worst grade
- Total number (number only) of TEAEs
- Deaths
- Subjects who discontinued study due to a TEAE
- Subjects who discontinued treatment due to a TEAE
- Subjects with a treatment-related TEAE resulting in treatment discontinuation
- Subjects with a treatment-emergent serious adverse event (SAE)
- Subjects with a treatment-related SAE
- Subjects with a treatment-related TEAE, overall and by worst grade
- Subjects with a COVID-19 related TEAE
- Subjects with a non-COVID-19 related TEAE

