11.2. Sample Size Calculation Details

The base sample size to have 90% power to detect a statistically significant reduction in the rate of hospitalization/death, given the study assumed rates of hospitalization, based on a one-sided 0.025 level test was computed using proc power is SAS (Version 9.4). This indicated that 991 subjects per arm (i.e. 1982 total subjects with 1:1 randomization). The corresponding code and output were:

```
proc power;
twosamplefreq test=pchi
power=0.9
groupproportions = (0.016, 0.04)
alpha=0.025
sides=1
npergroup=.
;
run;
```

The SAS System

The POWER Procedure Pearson Chi-square Test for Proportion Difference

Fixed Scenario Elements				
Distribution	Asymptotic normal			
Method	Normal approximation			
Number of Sides	1			
Alpha	0.025			
Group 1 Proportion	0.016			
Group 2 Proportion	0.04			
Nominal Power	0.9			
Null Proportion Difference	0			

Computed N per Group	
Actual Power	N per Group
0.900	991

The gsDesign function in the "gsDesign" package in R (Version 4.0.3) was used to identify the sample size adjustment and testing criteria needed to implement the planned interim analyses at 30% and 65% with O'Brien-Fleming spending for both alpha and beta (non-binding). The Lan-Demets spending function is used to approximate the O'Brien-Fleming boundaries (specified as sfLDOF in the code below). This indicated that a sample size inflation of 1.055 (at final) is needed for 90% power with overall type 1 error at one-sided 0.025 level. Total beta spending was specified at a 0.10 level. The corresponding code and output were:

```
Atea Pharmaceuticals, Inc.
                                                                                       Version 5
Statistical Analysis Plan - AT-03A-017
                                                                                   June 24, 2024
> gsDesign(k=3, test.type=4, alpha=0.025, beta=0.1, sfu=sfLDOF, sfl=sfLDOF, sflpar=-4, timing=c(0.3, 0.65,1))
Asymmetric two-sided group sequential design with
90 % power and 2.5 % Type I Error.
Upper bound spending computations assume
trial continues if lower bound is crossed.
          Sample
                  ----Lower bounds---- ----Upper bounds-----
          Size
 Analysis Ratio* Z Nominal p Spend+ Z Nominal p Spend++
        1 0.317 -0.96 0.1681 0.0027 3.93 0.0000 0.0000
        2 0.686 0.94 0.8262 0.0387 2.55 0.0054 0.0054
        3 1.055 1.99 0.9767 0.0587 1.99 0.0233 0.0196
                              0.1000
    Total

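### SAP 9.1 splits TEAEs but not SAEs by relation to COVID-19, so the total SAE row partly restates the efficacy result and can mask an offsetting excess of other SAEs on BEM

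*Protocol*

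**What the plan says.** **SAE definition.** Protocol 7.1 lists death as an SAE criterion and also "Requires inpatient hospitalization or prolongation of existing hospitalization". It has no exemption for events that are study endpoints.

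**Primary endpoint.** SAP 3.2.1 uses hospitalization or death from any cause through Day 29. Protocol 6.8 requires more than 24 hours of acute care and leaves out pre-planned admissions for a condition that has not worsened; it says such admissions are not SAEs either.

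**Safety window.** Under SAP 9.1 the treatment-emergent period runs from first dose to Day 29, the same horizon as the endpoint. Later events judged related are added.

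**Overall safety table (SAP 9.1).** One row is "Subjects with a treatment-emergent serious adverse event (SAE"; another counts subjects with a treatment-related SAE. TEAEs are also divided by relation to COVID-19, the second of those two rows being "Subjects with a non-COVID-19 related TEAE". No such pair exists for SAEs.

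**SOC and PT tables (SAP 9.2).** SAEs and deaths are each tabulated by system organ class and preferred term.

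**Context.** Protocol 1.7 describes SAEs in the earlier COVID-19 studies as "assessed as not related to study treatment, and tended to describe progression or complications of COVID-19". That concerns past studies, not this trial's tables, but it suggests what the SAE row here will mostly contain.

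**The concern.** Comparing the safety of BEM with placebo is a stated objective, and SAE incidence is a named safety endpoint. If the drug works as designed, fewer BEM subjects are hospitalized, and each hospitalization avoided is also an SAE avoided. The total SAE row then adds two quantities that may differ in sign: the efficacy effect, and any effect of BEM on other serious events. A level or favourable total could coexist with a rise in other SAEs. The SAP recognises the distinction for TEAEs but not for SAEs, where the overlap with the primary endpoint is greatest.

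**Working it through.** **1. Reproduce the design figures.** Inputs from SAP 4.3.1 and 11.2: "groupproportions = (0.016, 0.04" (BEM, placebo), one-sided alpha 0.025, "with 90% power at a 1-sided significance" level of 2.5%. A Pearson chi-square sample size with pooled variance and no continuity correction gives 991 per arm, 1982 in total, as stated. 1982 × 1.055 = 2091, stated as 2100; 2100 / 0.95 = 2210.5, stated as 2210. Evaluable subjects per arm: 2100 / 2 = 1050.

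**2. SAE subjects removed by efficacy.** Treat each endpoint subject as an SAE subject and the whole difference as a COVID-19 effect.

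| Placebo vs BEM | Placebo | BEM | Gap |
|---|---|---|---|
| 4% vs 1.6% | 1050 × 0.04 = 42.0 | 1050 × 0.016 = 16.8 | 25.2 subjects, 2.4 points |
| 3% vs 1.2% | 1050 × 0.03 = 31.5 | 1050 × 0.012 = 12.6 | 18.9 subjects, 1.8 points |

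The safety population does not require a positive swab. With up to 2210 / 2 = 1105 treated per arm, the gaps would be 26.5 and 19.9 subjects.

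**3. Total row against a separate row.** The documents give no background rate for other SAEs, so I assume 0.5%, 1% or 2% on placebo. Other-SAE subjects are taken as distinct from endpoint subjects, and the excess on BEM equals the gap of 2.4 points.

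| Assumed background | Total row, placebo vs BEM | Separate row, placebo vs BEM | Power of separate row, excess 2.4 points | Power, excess 1.8 points (at 3% vs 1.2%) |
|---|---|---|---|---|
| 0.5% | 4.5% vs 4.5% | 0.5% vs 2.9% | 99% | 94% |
| 1% | 5.0% vs 5.0% | 1.0% vs 3.4% | 96% | 86% |
| 2% | 6.0% vs 6.0% | 2.0% vs 4.4% | 88% | 69% |

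Power is for a two-sided 5% comparison with 1050 per arm. It is illustrative, since the SAP plans no SAE test. At a 1% background the Wald interval for the separate row uses SE = sqrt((0.034 × 0.966 + 0.010 × 0.990) / 1050) = 0.0064, so 2.4 ± 1.25 points, about 1.1 to 3.7. The total row would show a difference of zero.

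**4. When the excess is itself an endpoint event.** Non-COVID-19 hospitalizations and deaths count against BEM in the all-cause endpoint. The SAP removed the interim analyses, so fixed-design power applies. With 1050 per arm, placebo at 4% and one-sided 0.025:

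| Points added to BEM's 1.6% | BEM rate | Power for the primary test |
|---|---|---|
| 0 | 1.6% | 91.6% |
| 0.6 | 2.2% | 66% |
| 1.2 | 2.8% | 33% |
| 1.8 | 3.4% | 11% |

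An excess of this kind shrinks the effect that would do the masking. The full 2.4 points therefore needs SAEs that are neither endpoint hospitalizations nor deaths.

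**5. Can the non-COVID-19 TEAE row stand in?** It includes every non-COVID-19 SAE, but among non-serious events. As an illustration, take its placebo rate as 9.9%, the rate of all GI AEs on placebo in the earlier Phase 3 study (Protocol 1.2.1). An added 2.4 points gives z = 0.024 / sqrt((0.099 × 0.901 + 0.123 × 0.877) / 1050) = 1.75, power about 42%. It is less if some subjects with an SAE already had another TEAE.

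**The case against.** The strongest reply is that the planned output is richer than one total. SAP 9.1 has a treatment-related SAE row and a non-COVID-19 TEAE row, SAP 9.2 tabulates SAEs by SOC and PT, and SAP 6.1 lists all safety data. Protocol 7.2 tells sites to record secondary events by their primary cause, which helps keep COVID-19 progression apart from other terms. A DSMB reviews unblinded safety data. An excess of non-COVID-19 hospitalizations would also appear when the all-cause endpoint is set beside COVID-19-related hospitalization or death. And the total row is not wrong: it validly describes the net SAE burden in each arm.

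Much of this stands. A reader might infer that SAEs are compared only in total, or that an excess would be hidden across the whole report; SAP 9.1 and 9.2 contradict both. A reader might also take 2.4 points as an unconditional masking capacity, which step 4 rules out.

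A reader might see masking in the earlier Phase 3 study, where discontinuations for AEs were "2.8% in the BEM arm vs 7.0% in the placebo arm" although drug-related GI AEs were more frequent on BEM. Protocol 1.2.1 does not support that: the drug-related GI events were mild or moderate, none led to discontinuation, and no drug-related SAE was reported.

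What the reply leaves open is narrow. The treatment-related row rests on case-by-case causality, and Protocol 1.7 reports that earlier SAEs were judged unrelated, so it may be nearly empty. The SOC and PT tables spread a diffuse excess over many terms. Setting the two efficacy endpoints side by side uses mITT-S rather than the safety population and misses SAEs that are neither hospitalizations nor deaths. No planned row counts subjects with a non-COVID-19 SAE by arm.

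**Conclusion.** The point holds as a gap in one table. The total SAE row mixes efficacy with safety and can offset an excess of other SAEs of up to 2.4 points (about 25 per 1050) at 4% vs 1.6%, or 1.8 points (about 19) at 3% vs 1.2%.

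This assumes that endpoint events are all SAEs, that the design difference is all COVID-19 effect, and that the other SAEs fall in different subjects and are not endpoint events. The first is close but not exact, because Protocol 6.8 and 7.1 define hospitalization slightly differently. The power figures also depend on assumed background rates. Other planned outputs reduce the risk without replacing the missing count. This is an inexpensive improvement that should be made; it does not invalidate the safety analysis.

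**What to change.** In SAP 9.1 add two rows by arm and stratum: subjects with a COVID-19-related SAE and subjects with a non-COVID-19-related SAE. Give the risk difference with a 95% CI for the second. Use the flag already needed for the TEAE rows, and state who assigns it and that it is assigned under blinding; SAP 9.1 is silent on this, while SAP 8.7 already plans blinded medical review for complications. In SAP 9.2 add a table of non-COVID-19-related SAEs by SOC and PT. Keep the total SAE row and read the two together, so that the safety conclusion does not rest on the attributed row alone.

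The cost is two rows, one interval and one table, to be specified before unblinding. The downside is that the split depends on a case-by-case judgment that an event is due to COVID-19, which is a further reason to keep the total.

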2. STUDY OBJECTIVES

The primary objective is:

 To evaluate the efficacy of BEM compared with placebo in reducing all-cause hospitalization or all-cause death in COVID-19 outpatients receiving only supportive care.

The secondary objectives are:

- To evaluate the efficacy of BEM compared with placebo on:
 - COVID-19 related hospitalization or all-cause death through Day 29
 - All-cause death through Day 29 and Day 60
 - COVID-19-related complications (eg., death, hospitalization, radiologically confirmed pneumonia, acute respiratory failure, sepsis, coagulopathy, pericarditis/myocarditis, cardiac failure) through Day 29
 - COVID-19-related medically attended visits (hospitalization, emergency room (ER) visit, urgent care visit, physician's office visit, or telemedicine visit) or all-cause death through Day 29 and Day 60
 - COVID-19 symptom relapse
- To evaluate the antiviral activity of BEM compared with placebo on viral load rebound
- To evaluate the safety of BEM compared with placebo

The exploratory objectives are

- To evaluate the efficacy of BEM compared with placebo on:
 - Alleviation or improvement of individual COVID-19 symptoms
 - Return to usual (pre-COVID-19) health
 - Requirement for post-randomization rescue therapy
 - The antiviral activity of BEM compared with placebo
- To assess plasma concentrations of AT-511 (free base form of AT-527 [BEM]) and its metabolites from sparse PK sampling at steady-state

3. STUDY DESIGN

3.1. General Study Design

This Phase 3 randomized, double-blind, placebo-controlled study will be conducted in non-hospitalized adult subjects (≥18 years of age) with mild or moderate COVID-19 (as defined in inclusion criterion 3, Section 4.2) and risk factors for severe COVID-19 (as defined in inclusion criterion 8, Section 4.2).

Age and comorbidities will determine a patient's risk and eligibility (see inclusion criterion 8, Section 4.2). Onset of COVID-19 symptoms will have occurred ≤5 days before randomization.

BEM 550 mg or matching placebo will be administered BID for 5 days (10 doses, with each dose including 2 tablets).

Locally available SOC treatment should be initiated in parallel in addition to study drug (add-on). SOC treatments with direct antiviral activity against SARS-CoV-2 are allowed, but should be initiated during screening and/or within 24 hours prior to or after randomization.

Subjects will be randomized 1:1 (active:placebo) to one of the following arms:

- 550 mg BEM (2 x 275-mg tablets) BID for 5 days
- Placebo (2 tablets) BID for 5 days

Randomization will be stratified by geographic region (North America, Europe, Asia, and rest of world [ROW]), age (< 65 years old vs ≥ 65 years old) and by the type of SOC which the investigator plans to administer in parallel at time of study drug initiation. The type of SOC received will be used to classify subjects into two categories:

- a. Combination antiviral stratum (subsequently referred to as the combination antiviral population): In addition to study drug, the subject will be initiated on a local SOC regimen which includes a treatment with direct SARS-CoV-2 antiviral activity. Examples include nirmatrelvir/ritonavir, molnupiravir, favipiravir, mAbs,
- b. Supportive-care-only stratum (subsequently referred to as the supportive-care-only population): the SOC regimen the subject will receive does not include any treatment with direct SARS-CoV-2 antiviral activity.

Although randomization is stratified by whether COVID-19 drugs with antiviral effects are administered, both strata allow local SOC therapies without direct antiviral effects (ie corticosteroids).

Patients who require SOC treatment with a non-compatible antiviral treatment, defined as those with a potential DDI with BEM (eg, remdesivir), are excluded.

[figure not shown]
For subjects who deteriorate on-study, any rescue therapy which is SOC for progression to severe COVID-19 is permitted. As noted in Section 5.7.5, if rescue therapy will be remdesivir, study drug should be discontinued before initiation of remdesivir.

Approximately 2510 eligible subjects with COVID-19 will be enrolled, with a target of 2210 subjects in the supportive-care-only population and up to 300 subjects in the combination antiviral population. The primary study endpoint (hospitalization/death) will be evaluated in the supportive-care-only population.

The primary study period is up to 30 days, including up to 1 day for screening and 29 days from randomization. Extended follow-up data will be collected through Day 60 for mortality and medically attended visit assessment. The Day 60 follow-up contact marks the end of study participation for each subject and the study ends when the last subject completes the Day 60 follow-up contact.

A schematic of the study design is presented in Figure 1.

Figure 1: Study Design

This is a global clinical trial that complies with the European Union Clinical Trial Regulations (EU CTR). Results will be released to a publicly accessible web site (eg, Clinical Trial Information System [CTIS]) after the last European subject's completion of the study. However, if the study is ongoing outside the EU as of that date, results will be released after the last subject's completion date.

